5.0 STUDY CALENDAR

Pre-study Testing Intervals

The pre-study testing intervals are guidelines only. Laboratory and clinical parameters during treatment are to be followed using individual institutional guidelines and the best clinical judgment of the responsible physician. It is expected that patients on this study will be cared for by physicians experienced in the treatment and supportive care of patients on this trial.

When calculating days of tests and measurements, the day a test or measurement is done is considered Day 0. Therefore, if a test were done on a Monday, the Monday one week later would be considered Day 7.

To be completed ≤ 28 DAYS before registration: All laboratory studies, history and physical.

To be completed ≤ 42 DAYS before registration: Any X-ray, scan of any type or ultrasound which is utilized for tumor measurement per protocol.

To be completed ≤ 60 DAYS before registration: Any baseline exams used for screening, or any X-ray, scan of any type or ultrasound of uninvolved organs which is not utilized for tumor measurement.

	Prior to Registration*	Day 1 of each cycle*	Post-treatment follow up**	At PD, withdrawal, or removal**
Tests & Observations				
History and physical, weight, PS***	X	X	X	X
Pulse, Blood Pressure	X	X		
ECG	X(6)			
Adverse Event Assessment-CTCAE		X	X	
Adverse Event Assessment-PRO-CTCAE	X(1)	X(1)	X	
Registration Fatigue/Uniscale Assessment	X(2)			
Laboratory Studies				
Complete Blood Count, Differential, Platelets	X	X		
Serum Creatinine	X	X		
Albumin, glucose	X	X		
AST, ALT, Alk. Phos., Bili	X	X		
TSH with reflex T4		X		
Serum or Urine hCG	X(3)			
UPC ratio/urine protein	X	A		
Staging				
Tumor Measurement	X	C	X	
CT chest/abd/pelvis	X(5)	D	D	
Correlative studies				
QOL assessment	From baseline through 24 months, see Section 6.5 .			
Tissue, blood, and urine samples	See Section 6.2 .			

- * Labs completed prior to registration may be used for day 1 of cycle 1 tests if obtained \leq 14 days prior to treatment. For subsequent cycles, labs, scans, tests and observations may be obtained \leq 72 hours prior to day of treatment.
- ** Physical examination and staging scans are required \leq 12 weeks after the end of treatment, then every 12 weeks until disease progression; thereafter, survival information is required every 3 months until 3 years following registration. See also Section 12.0.
- *** Patients receiving immunotherapy will be assessed for pulmonary signs and symptoms throughout the study.

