7.2 Radiotherapy

Administration of radiotherapy will occur to a single site for subjects randomized to the pembrolizumab and radiotherapy group.

Radiotherapy can be initiated after the first dose of immunotherapy and must be completed before 12 weeks after first dose of immunotherapy administered.

There is no size criterion for irradiated site and should follow this priority list:

1. Growing area that may cause symptoms.
2. Area that can tolerate the highest dose prescription (8 Gy x 3) based on normal tissue constraints.
3. If all above equal, then order would be Pelvis, Abdomen, Liver, Lung, Bone.

The goal of RT treatment is to deliver appropriate radiotherapy while minimizing exposure of surrounding normal tissues. Many different ways of delivering RT exist, and all are acceptable as long as the treating institution has completed the necessary credentialing. Most commercially available electron and photon-producing treatment units are allowed. As such, conventional linear accelerators and specialized linear accelerators with image guidance (e.g., Novalis, Trilogy, Synergy, Artiste, TrueBeam, Unity, ViewRay) are allowed. These units can be used with conformal dose delivery or IMRT. Specialized dose painting accelerators (e.g., Cyberknife, or Tomotherapy) are allowed provided they meet the technical specifications of the protocol and are used in a fashion that passes the

credentialing required by the protocol. Conventional linear accelerators without add-on IGRT must have some other IGRT capability like CT-on-rails in the treatment room.

IGRT is required for this study. Either 3DCRT or IMRT (including VMAT) are acceptable planning techniques. IMRT (including VMAT) can result in dosimetric inaccuracies in circumstances where tumor motion is not properly considered. Planning techniques may differ for each lesion to be treated provided that the tumor motion is properly accounted for with each technique when the target or targets are in or near the thorax region.

i. Dose Fractionation

Patients will receive 3 fractions of radiation to a total dose of 24 Gy.

For each metastatic location, Variation Acceptable range is described for plan scoring. Doses falling outside the range of Per Protocol and Variation Acceptable will be scored as Deviation Unacceptable.

There should be a minimum of 40 hours between treatments to any single metastasis.

ii. Technical Factors

Physical Factors

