Although cardiac and pericardial injury is uncommon in the conventionally fractionated course of RT, with large doses per fraction of RT a number of possible side-effects can be seen.

Gastrointestinal/Esophageal Injury

The radiation effects on the esophagus can be acute: esophagitis (i.e., dysphagia, causing pain on swallowing, typically relatively soon after RT course is completed, and typically resolves on its own within days to a week or longer), or chronic, typically manifesting with dysphagia due to stenosis, or esophageal ulceration, with perforation in the extreme cases.

Central Airway/Bronchial Injury

This bronchial injury with subsequent focal collapse of lung may impair overall pulmonary status. It also makes further assessment of tumor response more difficult as the collapsed lung approximates the treated tumor. Because atelectatic lung and tumor have similar imaging characteristics, radiology reports will often describe the overall process as progressive disease, while the actual tumor may be stable or shrinking.

The consequences of bronchial toxicity, e.g., cough, dyspnea, hypoxia, impairment of pulmonary function test parameters, pleural effusion or pleuritic pain (associated with collapse), should all be graded according to the Common Terminology Criteria for Adverse Events (CTCAE), v. 4; MedDRA, v. 12.0.

Lung Injury

Radiation pneumonitis is a subacute (weeks to months from treatment) inflammation of the end bronchioles and alveoli. Radiation fibrosis is a late manifestation of radiation injury to the irradiated lung. Given the small amount of lung that is typically included in the SBRT portals, lung toxicity has

not been as dose-limiting as in conventionally fractionated, large-field RT, but it is nevertheless seen, can be symptomatic, and may be confused with other causes of respiratory deterioration, including infections, and tumor recurrence.

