Less likely, but serious (<20%): Patients may experience radiation-induced liver disease (RILD) (<5%). Classic RILD is a clinical diagnosis of anicteric ascites, hepatomegaly and elevation of alkaline phosphatase relative to other transaminases that may occur 2 weeks to 3 months following radiation to the Liver; non-classic RILD includes elevation of liver enzymes and/or any decline in liver function within 12 weeks from start of therapy (~20%). RILD can lead to liver failure that could lead to death. There is an increased risk of liver toxicity in patients with large tumors and in patients with pre-existing liver disease. In addition, permanent thrombocytopenia (<1%) may lead to bleeding, and kidney injury (<1%) may lead to changes on imaging and more rarely the need for medication.

Spinal metastases

Radiation Myelitis

Given the proximity and position of the spinal cord in relation to the radiosurgery target, every effort should be made to minimize the radiation dose to the spinal cord. Radiation myelitis is a subacute or chronic clinical syndrome after radiation. The symptoms may include paresthesia, sensory changes, and motor weakness including paralysis. There is no active treatment for radiation myelitis; therefore, it is important to prevent any injury to the spinal cord. Corticosteroids are used when clinical symptoms develop.

Radiation Esophagitis

Patients with thoracic spine treatment will likely develop esophageal mucositis within the first 2 weeks. These symptoms subside with time; however, adequate symptomatic treatment including hydration is advised. There are no long-term adverse events reported with spine radiosurgery. However, it is prudent to minimize the radiation spillage in the normal esophagus. The consequences of esophageal toxicity, e.g., swallowing difficulty, dysphagia, cough, dehydration, and fistula, should be documented.

Radiation Laryngitis or Pharyngitis

Patients with cervical spine treatment will likely develop laryngopharyngeal mucositis within the first 2 weeks. These symptoms subside with time; however, adequate symptomatic treatment including hydration is advised. No long-term laryngopharyngeal toxicity has been reported with spine radiosurgery. However, it is prudent to minimize the radiation spillage in the normal larynx and

pharynx. The consequences of toxicity, e.g., swallowing difficulty, dysphagia, cough, dysphonia, dehydration, and fistula, should be documented.

Tracheal Injury

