8.2.1 General AE Management and Dose Modification Guidelines for Pembrolizumab (MK-3475)

Dose Modifications

Adverse events (both nonserious and serious) associated with pembrolizumab exposure may represent an immunologic etiology. These AEs may occur shortly after the first dose or several months after the last dose of treatment. Pembrolizumab must be withheld for drug-related toxicities and severe or life-threatening AEs as described below.

Dosing interruptions are permitted in the case of medical/surgical events or logistical reasons not related to study therapy (e.g., elective surgery, unrelated medical events, patient vacation, and/or holidays). Patients should be placed back on study therapy within 3 weeks of the scheduled interruption. The reason for interruption should be documented in the patient's study record.

Dose Modification and Toxicity Management for Immune-related Adverse Events Associated with Pembrolizumab

AEs associated with pembrolizumab exposure may represent an immunologic etiology. These immune-related AEs (irAEs) may occur shortly after the first dose or several months after the last dose of pembrolizumab treatment and may affect more than one body system simultaneously. Therefore, early recognition and initiation of treatment is critical to reduce complications. Based on existing clinical study data, most irAEs were reversible and could be managed with interruptions of pembrolizumab, administration of corticosteroids and/or other supportive care. For suspected irAEs, ensure adequate evaluation to confirm etiology or exclude other causes. Additional procedures or tests such as bronchoscopy, endoscopy, skin biopsy may be included as part of the evaluation. Based on the severity of irAEs, withhold or permanently discontinue pembrolizumab and administer corticosteroids. Pembrolizumab may cause severe or life-threatening infusion-reactions including severe hypersensitivity or anaphylaxis. Signs and

symptoms usually develop during or shortly after drug infusion and generally resolve completely within 24 hours of completion of infusion. Dose modification and toxicity management guidelines for irAEs and infusion reactions associated with pembrolizumab are provided in the table below.

Note that non-irAEs will be managed as appropriate, following clinical practice recommendations.

Table for Dose Modification and Toxicity Management Guidelines for Immune-related AEs and Infusion Reactions Associated with Pembrolizumab

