9.2 CTCAE Routine Reporting Requirements

In addition to the solicited adverse events listed in [Section 9.1](#), the following table outlines the combinations of time points, grades and attributions of AEs that require routine reporting to the Alliance Statistics and Data Center. Questions about routine reporting should be directed to the Data Manager.

Combinations of CTCAE Grade & Attribution Required for Routine AE Data Submission on Case Report Forms (CRFs)

Attribution	Grade 1	Grade 2	Grade 3	Grade 4	Grade 5
Unrelated			a	a	a
Unlikely			a	a	a
Possible			a, b	a, b	a, b
Probable			a, b	a, b	a, b
Definite			a, b	a, b	a, b

- a) **Adverse Events: Other CRF** - Applies to AEs occurring between registration and within 30 days of the patient's last treatment date, or as part of the Clinical Follow-Up Phase.
- b) **Adverse Events: Late CRF** - Applies to AEs occurring greater than 30 days after the patient's last treatment date.

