12.3 Follow-up

12.3.1 Duration of Follow-up: Physical examination and staging scans are required within 12 weeks after the end of treatment, then every 12 weeks until disease progression; thereafter, survival information is required every 3 months until 3 years following registration.

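### For patients who stop treatment at progression, scheduled adverse-event assessment is not secured, so AE observation windows depend on progression

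*Combined protocol and SAP*

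**What the plan says.** **Calendar (Section 5.0).** The rows "Adverse Event Assessment-CTCAE" and "Adverse Event Assessment-PRO-CTCAE" are marked on Day 1 of each cycle and at post-treatment follow-up. Both are blank in the column for PD, withdrawal or removal, although history and physical examination is marked there. Section 9.1 ties routine AE reporting to this calendar.

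**Follow-up (Section 12.3.1 and the calendar's double-asterisk footnote).** Examination and scans are due within 12 weeks of the end of treatment, "then every 12 weeks until disease progression; thereafter, survival information is required every 3 months until 3 years following registration". The sentence does not mention AEs; its bearing on them comes from reading it with the calendar. Section 12.3.2 says that patients on non-protocol therapy are followed for events, but defines neither the events nor a schedule.

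**Timing.** Radiotherapy "must be completed before 12 weeks after first dose of immunotherapy administered" (Section 7.2). Section 11.0 sets re-evaluation every 12 weeks from Cycle 1 Day 1.

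**Late risks the protocol itself describes.** Under Radiation Therapy Adverse Events in Section 7.2, classic radiation-induced liver disease "may occur 2 weeks to 3 months following radiation to the Liver", and "Radiation pneumonitis is a subacute (weeks to months from treatment) inflammation". On pembrolizumab, Section 8.2.1 says: "These AEs may occur shortly after the first dose or several months after the last dose of treatment".

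**Reporting forms (Section 9.2).** Grade 3-5 events of any attribution are collected up to 30 days after last treatment "or as part of the Clinical Follow-Up Phase". After 30 days, a Late form takes Grade 3-5 events that are at least possibly related.

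**Analysis (Section 13.7).** CTCAE events are summarised by arm as the maximum grade per patient, with no stated window. Maximum post-baseline PRO-CTCAE scores over 24 months are tested between arms at a nominal 0.10.

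**The concern.** The latest permitted end of radiotherapy and the first scan nearly coincide. A patient whose scan shows progression and who stops then moves to a follow-up stage in which no AE assessment is clearly scheduled, just as the described late effects could begin. Reporting rules say what to do with an event once it is known; they do not schedule anyone to ask.

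The second issue is comparability. How long a patient is actively observed for AEs depends on when that patient progresses and stops, and the arms are compared on progression. If radiotherapy delays progression, Arm B is watched longer and has more opportunity to record events. If it does not, radiotherapy effects that appear late, and only in Arm B, may fall outside scheduled observation. These act in opposite directions, and the documents do not show which would dominate. Either way, objective 2.2.4 would be answered over windows that are neither fixed nor independent of outcome.

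**Working it through.** The plan gives no figure to reproduce here; the check is date arithmetic on its own schedule. Conventions: Cycle 1 Day 1 = day 0, and 3 months = 91 days.

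1. **Latest radiotherapy finish.** Before 12 weeks: 12 × 7 = 84, so day 83 at the latest (Section 7.2).
2. **First scan.** Day 84 under Section 11.0. Section 6.4.1 instead gives 3 months ± 14 days: 91 − 14 = 77 to 91 + 14 = 105.
3. **Cycle visits.** Every 21 days: days 0, 21, 42, 63, 84. If a patient stops on a day-84 scan, the last Day-1 AE assessment is on day 63 (83 − 63 = 20 days before the last fraction), or on day 84 (1 day after it) if that visit takes place.
4. **Liver-injury window after a day-83 finish.** From 83 + 14 = day 97 to 83 + 91 = day 174. All of it follows day 84, and it ends 174 − 84 = 90 days after progression. If progression is found at the late end of the scan window, 174 − 105 = 69 days remain.
5. **What Section 12.3.1 then schedules.** Two readings are possible.
   - *Progression ends all post-treatment visits.* No AE assessment is scheduled after day 84.
   - *Progression ends only the repeat visits.* One visit is still owed by 83 + 84 = day 167, with no earliest date. Held before day 97, it sees none of the liver window; held on day 167, it leaves 174 − 167 = 7 days uncovered. Nothing scheduled must follow it.
6. **What the reporting rules cover.** With last treatment on day 83, the 30-day any-attribution period ends on 83 + 30 = day 113. For the remaining 174 − 113 = 61 days, the certain coverage is the Late form for related Grade 3-5 events and the related-SAE rule in Section 9.3.1. Neither brings a scheduled contact.
7. **PRO-CTCAE maximum scores.** A patient who stops at day 84 has at most 4 post-baseline Day-1 assessments (days 21, 42, 63, 84). A patient on treatment for 24 months (730 days) has 34, since 730 / 21 = 34.8. A maximum taken over more assessments can only stay the same or rise. A test of the proportion whose maximum exceeds a threshold therefore partly reflects how long each arm was assessed. By contrast, Section 12.3.3 continues the QOL forms after progression.

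**The case against.** The strongest reply has five parts.

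- **The follow-up sentence can be read as owing one visit after any end of treatment.** This stands as a fair reading, so a flat statement that the patient has no AE visit after radiotherapy would be wrong. Even so, that visit may come before the whole risk window.
- **Reporting does not stop at progression.** This stands. Related Grade 3-5 events, related SAEs and related deaths after 30 days (Sections 9.2, 9.3.1 and 9.3.4) and all new malignancies remain reportable. What is exposed is active questioning, Grade 1-2 events, unrelated events after 30 days, and PRO-CTCAE.
- **Contacts still exist.** This stands: there is 3-monthly survival contact, an examination at PD or removal, and QOL forms for consenting patients. None is stated to include an AE question, but they make the remedy cheap.
- **Patients treated beyond progression are unaffected.** This stands: Section 7.1 allows it, and their Day-1 assessments continue.
- **The example is extreme, and some material is missing.** This stands in part. Radiotherapy may begin after the first dose, and patients irradiated early have weeks of cycle visits before the first scan. The Data Submission Schedule named in Section 6.1.1 is not supplied, and the clinical follow-up phase in Section 9.2 is undefined, so its closing at progression is an inference.

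A reader might infer that AE collection ends at progression and that Arm B's harm will be understated. The documents do not support that: the reporting duties above continue, and the possible biases run both ways. Nor does Section 13.7 test CTCAE rates between arms; it summarises them. Only the PRO-CTCAE comparison is a test.

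**Conclusion.** The point holds for patients who stop treatment at progression. As written, the plan secures them at most one later AE assessment, at an uncontrolled time, while the protocol describes liver, lung and immune effects arising weeks to months after treatment. In the worst case, with radiotherapy ending on day 83 and progression found on day 84, the full liver-injury window (days 97 to 174) comes after progression. On the stricter reading of Section 12.3.1 no scheduled assessment falls in it.

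The consequence is incomplete active detection and AE windows that depend on outcome. This affects the by-arm CTCAE summary and, more directly, the tested PRO-CTCAE maximum scores over 24 months. The direction of any bias cannot be stated.

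The number of patients affected cannot be derived either, because the documents give no progression-free survival assumption and no expected distribution of radiotherapy timing. The day counts rest on the 91-day convention and on the latest permitted radiotherapy finish. The primary endpoint is untouched. The change should be made because it is specific and inexpensive.

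**What to change.** 1. **Section 5.0:** mark CTCAE and PRO-CTCAE assessment in the PD/withdrawal/removal column, where an examination is already required.
2. **Sections 5.0 and 12.3:** require an AE contact at 30 days and at about 90 days after the last pembrolizumab dose or radiotherapy fraction, whichever is later, regardless of progression. A telephone call is enough, combined with the 3-monthly survival contact where possible. State whether the post-treatment visit within 12 weeks is owed after progression.
3. **Sections 9.2 and 13.7:** define one fixed AE window, the same in both arms, for collection and for the by-arm tables. Define the clinical follow-up phase.
4. **PRO-CTCAE:** either continue it after progression on the QOL schedule (Section 12.3.3), or restrict the Section 13.7 comparison to the common window.
5. Reconcile Sections 5.0, 9.2, 12.3.1, 12.3.2 and 13.7 so that they describe the same follow-up.

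The cost is wording in the calendar and case report forms, up to two short contacts per patient, and the work of attributing events that occur after new therapy has started. The 90-day contact will often coincide with a survival contact.

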12.3.2 Follow-up for Patients who Stop Study Treatment/Intervention Early

Follow up for patients who receive non-protocol therapy will be for event monitoring

12.3.3 Follow-up for Specimen and QOL Submission

QOL measures are to be completed at baseline, and at 45 days, and at 6, 12, and 24 months following registration. **Measures should continue to be submitted following progression.**

12.4 Extraordinary Medical Circumstances

If, at any time the constraints of this protocol are detrimental to the patient's health and/or the patient no longer wishes to continue protocol therapy, protocol therapy shall be discontinued. In this event:

- Document the reason(s) for discontinuation of therapy on data forms.
- Follow the patient for protocol endpoints as required by the Study Calendar.

12.5 Managing ineligible patients and registered patients who never receive protocol intervention

Definition of ineligible patient

A study participant who is registered to the trial but does not meet all of the eligibility criteria is deemed to be ineligible.

Follow-up for ineligible patients who continue with protocol treatment

Patients who are deemed ineligible after registering may continue protocol treatment, provided the treating physician, study chair, and executive officer agree there are no safety concerns if the patient continues protocol treatment. No further follow-up will be required for these patients. Notification of the local IRB may be necessary per local IRB policies.

Follow-up for ineligible patients who discontinue protocol treatment

For patients who are deemed ineligible after registering to the trial, who start treatment, but then discontinue study treatment, the same data submission requirements are to be followed as for those patients who are eligible and who discontinue study treatment.

Follow-up for patients who are registered, but who never start study treatment

For all study participants who are registered to the trial but who never receive study intervention (regardless of eligibility), no follow-up will be required.

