4.6.2 Treatment Assignments

Patients will be randomized 1:1 to the two treatment arms. The factors defined in [Section 4.8.1](#) will be used as stratification factors.

After the patient has been registered into the study, the values of the stratification factors will be recorded, and the patient will be randomized to one of the following treatment groups using the Pocock and Simon dynamic allocation procedure which balances the marginal distributions of the stratification factors between the treatment groups.

- 1) Immunotherapy
- 2) Immunotherapy + Single Site Radiotherapy

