6.4 Imaging Data Submission Methods

Data must be submitted according to the protocol requirements for ALL patients registered, whether or not assigned treatment is administered, including patients deemed to be ineligible.

DICOM images uploading is preferred to be submitted using TRIAD, however these methodologies are supported:

- a. TRIAD-based (a PC with internet access and TRIAD software installation will be needed)
- b. Web transfer-based (a PC with internet access and a web browser will be needed)
- c. FTP transfer-based (a PC with internet access and any FTP software will be needed)
- d. Mail/CD Shipment-based (only if electronic transfer approaches cannot be achieved)

Questions regarding image submissions can be sent to [contact].

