7.0 TREATMENT PLAN/INTERVENTION

Protocol treatment is to begin ≤ 14 days of registration.

For questions regarding treatment, please see the study contacts page.

Patients must have completed last systemic cancer therapy within 4 weeks prior to the start of protocol treatment.

It is acceptable for individual chemotherapy doses to be delivered \leq a 24-hour (business day) window before and after the protocol-defined date for Day 1 of a new cycle. For example, if the treatment due date is a Friday, the window for treatment includes the preceding Thursday through the following Monday. In addition, patients are permitted to have a new cycle of chemotherapy delayed up to 7 days for major life events (e.g., serious illness in a family member, major holiday, vacation that cannot be rescheduled) without this being considered a protocol violation. Documentation to justify this delay should be provided.

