13.6 Primary Analysis Plan

Interim analysis for futility: There will be one interim analyses for futility. The interim analysis will occur after 50% of the patients (i.e. 68) have been followed for six months. If at this time the tumor response for Arm A (immunotherapy alone) is greater than the tumor response rate for Arm B (immunotherapy plus radiation), which would correspond to an OR > 1, the recommendation will be to stop the trial due to futility.

Final Analysis: The final analysis will occur after 136 evaluable patients have completed 6 months of follow-up. The tumor response rate will be analyzed with a Mantel-Haenszel test (that accounts for the randomization stratification factors) comparing the response rates between the two treatment arms. The analysis will be a modified intent-to-treat analysis where patients are ineligible or not evaluable will be excluded. An additional analysis will be conducted using logistic regression analysis that includes treatment arm and any baseline variables that are imbalanced between the arms as explanatory variable.

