14.1.4 Statistical Considerations

All questionnaires will be scored according to published scoring algorithms, including recommendations for addressing missing items within a scale. An intent-to-treat approach will be used for all analyses. To evaluate between-arm differences in patient-reported fatigue from baseline through 24 months, the area under the curve will be calculated as a summary statistic for each arm based on estimates from a mixed model for patient-reported fatigue as assessed by the PROMIS-Fatigue 8a at baseline, at 45 days, and at 6, 12, and 24 months. This approach of estimating each arm's area under the curve as a summary statistic (rather than each patient's area under the curve as a summary measure) is recommended for addressing missing data over time²⁷. The mixed model will include a fixed intercept; fixed effect for time, arm, and arm by time interaction; and residual covariance matrix based on the observed covariances. An unstructured residual covariance matrix will initially be used, though alternative structures will be investigated with final selection based on convergence of the mixed model and minimization of the Akaike information criterion. Stratification factors used in the randomization as well as baseline patient characteristics and prognostic factors may be included in the mixed model as covariates. Estimates from the mixed model will be used to construct a 90% confidence interval for the difference in area under the curve between arms. The contrast estimated via the mixed model will involve a two-sided *t*-test with a nominal significance level of $\alpha = .10$.

To evaluate between-arm differences in HRQOL from baseline through 24 months, the area under the curve will be calculated as a summary statistic for each arm based on estimates from a mixed model for HRQOL as assessed by the EORTC QLQ-C30 at baseline, at 45 days, and at 6, 12, and 24 months. Estimates from the mixed model will be used to construct a 90% confidence interval for the difference in area under the curve between arms. The contrast estimated via the mixed model will involve a two-sided *t*-test with a nominal significance level of $\alpha = .10$.

To evaluate between-arm differences in urinary symptoms from baseline through 24 months for patients with a urostomy, the area under the curve will be calculated as a summary statistic for each arm based on estimates from a mixed model for urinary symptoms as assessed by the

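### Section 12.5 waives follow-up for some randomized patients, conflicts with Section 6.4, and leaves PFS, OS, QOL and discontinuation data incomplete, with no all-randomized check on response

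*Combined protocol and SAP*

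**What the plan says.** **Who is randomized.** Section 4.6.2: "After the patient has been registered into the study, the values of the stratification factors will be recorded, and the patient will be randomized". A registered patient is therefore a randomized patient. Section 7.0 leaves a gap before treatment: "Protocol treatment is to begin ≤ 14 days of registration". Section 13.1 describes the trial as open-label.

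**Who is followed (Section 12.5).** There are three rules:
- Never treated: for those "who never receive study intervention (regardless of eligibility), no follow-up will be required".
- Ineligible but continuing protocol treatment: "No further follow-up will be required for these patients".
- Ineligible, started and then stopped: "the same data submission requirements are to be followed as for those patients who are eligible and who discontinue study treatment".

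**What Section 6.4 requires.** Imaging data must be submitted "for ALL patients registered, whether or not assigned treatment is administered, including patients deemed to be ineligible".

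**Which populations are analysed.**
- Response (13.6): "The analysis will be a modified intent-to-treat analysis where patients are ineligible or not evaluable will be excluded". Not evaluable is not defined there.
- PFS and OS (13.2.2) are timed from randomization. Section 13.7 names no population for them.
- One-year discontinuation (13.7): the denominator starts from all patients randomized to the arm and keeps those alive and progression-free at one year.
- Quality-of-life substudy (14.1.4), including quality-adjusted survival: "An intent-to-treat approach will be used for all analyses".

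**The concern.** Two groups of randomized patients may leave the trial with no outcome recorded: those who never start treatment, even if fully eligible, and ineligible patients who stay on protocol treatment. Section 6.4 names the same kinds of patient and asks for their data, so a site cannot tell which rule governs. Section 12.5 is also uneven within itself: an ineligible patient who stops treatment must submit full data, while one who continues need not.

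At stake is the comparison as randomized. Up to 14 days may pass between registration and treatment, with the arm known, so failure to start could depend on the arm and on prognosis. Vital status and progression that are not collected may not be recoverable later. For response, the plan has no analysis that would show whether the modified intent-to-treat result depends on who was left out.

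**Working it through.** **1. The plan's own sample size.** Inputs from Section 13.4: one-sided alpha 0.10, power 90%, response 20% v 40%, 1:1 allocation. With z = 1.2816 for both alpha and power, and mean rate 0.30:

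n per arm = [1.2816·√(2·0.30·0.70) + 1.2816·√(0.20·0.80 + 0.40·0.60)]² / 0.20² = 67.3, rounded up to 68.

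The total is 136, as stated. Inflation: 136/0.95 = 143.2, rounded up to 144, as stated. Power at 68 per arm is 90.2%, or about 89.9% by simulation once the futility stop is included.

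**2. How many patients are affected.** The documents give no number. The 5% allowance (144 − 136 = 8) is for all ineligible or non-evaluable patients. That includes ineligible patients who stop treatment, whose data are still required, and could include treated patients without usable scans. I use 8 only as an assumed figure for exclusions.

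**3. What exclusion could do to the response test.** Assumptions: 72 randomized per arm, true response 20% in both, every excluded patient a non-responder, pooled z-test at one-sided 0.10, no stratification, no interim stop. Expected responders per arm are 0.20 × 72 = 14.4, and the expected observed rate is 14.4/(72 − number excluded). Rejection probabilities are by exact enumeration of both binomials.

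| Excluded in A / B | Observed rate A | Observed rate B | Type I error |
|---|---|---|---|
| 0 / 0 | 20.0% | 20.0% | 10.1% |
| 4 / 4 | 14.4/68 = 21.2% | 21.2% | 10.1% |
| 3 / 5 | 14.4/69 = 20.9% | 14.4/67 = 21.5% | 12.3% |
| 0 / 4 | 20.0% | 21.2% | 13.3% |
| 0 / 8 | 20.0% | 14.4/64 = 22.5% | 17.5% |
| 8 / 0 | 22.5% | 20.0% | 5.5% |

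The error moves with the imbalance between arms. Balanced exclusion leaves it at nominal, and exclusion from Arm A alone makes the test conservative.

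**4. Which section causes this.** The shift in the table comes from the exclusion rule in 13.6. If follow-up were collected under 12.5 and 13.6 stayed as it is, the primary type I error would not change. What 12.5 removes is the outcome data for PFS, OS, quality of life and the discontinuation denominator, where status at one year must be known.

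**5. Power if everyone randomized is counted.** 72 per arm, a share m unassessed in each arm (assumed equal) and counted as non-responders, so the rates become 0.20(1 − m) and 0.40(1 − m). Normal approximation, no interim stop:

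| m | Counted as non-responders | Excluded |
|---|---|---|
| 0 | 91.5% | 91.5% |
| 5% | 89.8% (19% v 38%) | 90.4% |
| 10% | 88.0% | 89.1% |

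**The case against.** The strongest case against has five parts.

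- **The waiver for ineligible patients fits the primary analysis.** Section 13.6 openly specifies a modified intent-to-treat analysis that leaves them out. This stands for response. It does not cover eligible patients who never start, nor PFS, OS and the discontinuation rate, for which no reduced population is named.
- **The intent-to-treat analyses remain feasible.** A reader might infer that the waivers make them impossible. The documents do not support that. The only unmodified intent-to-treat statement is in the optional quality-of-life substudy. Its mixed models can use patients with baseline data only under missing at random, and Section 14.1.4 promises a missing-data sensitivity analysis. PFS and OS can be censored at last contact. Response with no assessment counted as non-response needs only arm and stratum, both recorded at randomization.
- **Arm-dependent non-starting is not shown.** Both arms begin with pembrolizumab, and radiotherapy comes after the first dose (7.1, 7.2). An Arm B patient who takes pembrolizumab and declines radiotherapy has received study intervention and is outside the never-treated waiver. This makes a strong imbalance less likely; it does not exclude one.
- **The conflict with 6.4 may be softer than it looks.** Section 6.4 concerns imaging and asks for submission according to protocol requirements, so it could mean only scans required elsewhere, such as baseline. That reading is available, but a site should not have to choose it.
- **Not required does not mean forbidden.** True, but data that nobody must collect cannot be relied on.

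**Conclusion.** The point holds as a conflict between sections and a gap in required data. Sections 12.5 and 6.4 must be reconciled. Following 12.5 as written leaves PFS, OS, the quality-of-life analyses and the discontinuation rate incomplete and open to bias for an unstated, probably small, number of randomized patients. Separately, 13.6 does not classify an eligible, never-treated patient and offers no all-randomized check on response.

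Under the assumptions in the working, 8 excluded patients give a type I error anywhere from about 5.5% to 17.5%. The upper end is a worst case, with all 8 being Arm B non-responders, and is not a forecast. It would also be wrong to read the 5% allowance as the plan's own count of waived patients, or to expect a change to 12.5 alone to remove the bias. The point is worth correcting because the remedy is cheap and the missing outcomes may not be recoverable later.

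**What to change.** 1. **Sections 12.5 and 6.4:** reconcile them. Require survival and progression status, and submission of any scans obtained, for all randomized patients where consent allows, whether or not they are eligible or treated.
2. **Section 13.6:** define not evaluable, and state that eligible patients who never start treatment count as non-responders. Add a sensitivity analysis of response in all randomized patients, with no assessment counted as non-response.
3. **Section 13.7:** state that PFS and OS are analysed in all randomized patients.

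**Cost.** Contact and data collection for a small number of patients for up to 3 years, and a small loss of power in the all-randomized response analysis: about 89.8% with 5% unassessed in each arm, against 90.4% if they are excluded. The target of 144 need not rise.
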